4.2 Outcomes

Primary endpoints:

1. Proportion of lung cancers detected with different risk models

To address the suitability of different inclusion methods for identifying the high-risk population for screening, the PLCO_M2012 model and the NELSON inclusion criteria will be compared primarily for the positive predictive value of lung cancers detected within the study population after 2 screening rounds.

Key-Secondary endpoints:

Additionally, the PLCO_M2012 model and the NELSON inclusion criteria will be compared in a hierarchical order regarding the key secondary endpoints:

1. Proportion of individuals selected for screening within the high-risk study population
2. Proportion of lung cancers detected with different inclusion methods (NELSON vs. PLCO) within the overall study population after 5 years
3. Proportion of lung cancers detected within the high-risk population
4. Sensitivity within the overall population after 5 years.

5. Specificity within the overall population after 5 years.

Secondary endpoints:

6. **Rate of initiation of cardiovascular treatments** (in particular lipid-lowering) in the calcium score reporting group vs. the non-reporting group after year 1 of study.
7. **Efficiency of nodule management algorithms:** Based on the two alternative management algorithms (LungRads1.1 alone or LungRads1.1 + PanCan/AI) participants are sorted into three management groups: (a) next surveillance scan, (b) early recall scan, or (c) diagnostic evaluation recommended. For one algorithm to be more efficient, the following criteria must both be fulfilled
 - i. The number of participants without cancer sorted in the category (a) is higher AND
 - ii. The number of participants with lung cancer sorted into category (b) or (c) is higher.
8. **Success of screening program.** Based on all individuals enrolled. Definition of success is calculated using:
 - a. Response rate (1. Respondents to questionnaire / invitation: those who send their smoking history & other relevant data; 2. among the above respondents, those who are eligible by one of the two criteria, or both; 3. those who are eligible, and actually take part in the screening), number of drop-outs, effectiveness of patient recruitment via mailings vs. GPs referrals (individual response rates)
 - b. Reliability of PLCO risk scoring (self-reported vs. on site assessment)

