For testing the null-hypothesis of no difference between the risk scores regarding the proportion of individuals selected for screening, McNemar's Test will be used.

Description of the primary analysis and population:

The primary analysis will be conducted of all volunteers within the overall study population after 2 LDCT screening rounds.

5.1.2 Secondary Objective(s): Calculation of Epidemiological Measure(s) of Interest (e.g. hazard ratios, incidence rates, test/retest reliability)

1. Rate/rate ratio of initiation of cardiovascular treatments (in particular lipid-lowering) in the calcium score reporting group vs. the non-reporting group after year 1 of study:

2. Efficiency of nodule management algorithms:

Based on the two alternative management algorithms (LungRads1.1 alone or LungRads1.1 + PanCan) patients are sorted into three management groups: (a) next surveillance scan, (b) early recall scan, or (c) diagnostic evaluation recommended. For one algorithm to be more efficient, the following criteria must both be fulfilled

- i. The number of patients without cancer sorted in the category (a) is higher AND
- ii. The number of patients with lung cancer sorted into category (b) or (c) is higher.

3. Success of screening program. Based on all individuals enrolled. Definition of success is calculated using:

a. Response rate (number of responses/overall number contacted), number of drop-outs, effectiveness of patient recruitment via mailings vs. GPs referrals (individual response rates)

b. Percentage of subjects meeting all inclusion/exclusion criteria

c. Repeatability of the PLCO score

d. Percentage of subjects receiving an adequate low-dose CT scan according to DRG guidelines (number of diagnostic CTs/number of all CTs)

4. Quality of screening program.

a. CT reading performance (2nd reader vs. CAD vs. AI)

b. Frequency of detection and management of incidental findings from low dose chest CT (emphysema, coronary heart disease, etc.)

c. Subsequent identification of biomarkers with predictive value / correlation with positive LDCT findings / cancer risk

5. Smoking cessation

a. Success of smoking cessation counseling based on number of participants quitting with or without revealing additional health risks (emphysema score, coronary calcium score or both).

6. Blood-based and exhalation- based biomarkers

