- Non-qualifying subjects (who did not meet the NELSON inclusion criteria or PLCO criteria) will be asked to volunteer by contributing long-term outcome data informing of the development of lung cancer or death from lung cancer. In addition NELSON and PLCO non-qualified subjects with a smoking history, who volunteered to participate in the HANSE study, will be contacted via mail after 5 years to inquire if they developed lung cancer in the time between their recruitment and present. Non-responders will be followed by local cancer registries and by phone.

2. **LDCT - 1. Screening round**

- **Lung function test:** All included participants will receive a lung function test prior to undergoing LDCT.
- **Cardiovascular health:** All participants will be questioned whether they receive treatment for any cardiovascular conditions. Blood pressure, heart rate and BMI data (height and weight) will be obtained.
- Assessment of current **COPD treatment medication.**
- **Randomization:** Subjects included in the screening study will be randomized prior to receiving the initial LDCT scan. Randomization will not affect the procedure and the schedule of the cancer screening process but only determine the allocation of the participants of the coronary calcium score and emphysema score to the reporting and the non-reporting group. Randomization ratio of 1:1 and a 2-factorial design ($\frac{1}{4}$ calcium score only; $\frac{1}{4}$ emphysema score only, $\frac{1}{4}$ both; $\frac{1}{4}$ none) will provide equally sized groups of patients in both groups including age (5 year groups) and sex stratification .

Lung LDCT assessment:

- **Standardized and quality-assured image analysis** will be conducted using state-of-the-art artificial intelligence (AI)-based detection and nodule measurement software (Coreline) to support the radiologist. CT assessment of lung nodules will be performed according to LungRADS 1.1 criteria (see Appendix), as well as volume doubling time according to the European position statement on lung cancer screening (14).
- Inspection of **lungs for nodules** will be carried out for all subjects, independent of the assigned groups (reporting or non-reporting).
- An independent 2nd read by an additional radiologist using the same reading software algorithm will be performed.
- Subjects with no nodules or those of LungRADS grades 1, 2, 3, 4a will be scheduled for follow-up scans at intervals according to LungRADS schedule (see Appendix).

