- Findings categorized as LungRADS Cat. 4b or 4X nodules will be presented to the local Multidisciplinary Tumor Board (MDT) for further assessment and treatment decisions in the clinical routine workflow.
- **Emphysema** severity as a measure for tobacco related lung destruction will be quantitatively assessed on the LDCT images using the fully automated artificial intelligence (AI)-based algorithm of the Coreline software (Coreline, Seoul South Korea). The data will either be reported to study participants and treating physicians or not according to the allocation of the individual to the two randomized experimental groups.
- **Coronary calcium scores** (Agatston score) will be assessed using the fully automated artificial intelligence (AI)-based algorithm of the Coreline software (Coreline, Seoul South Korea). However, only the reporting group will receive the results of the score, together with an explanation of potential consequences of these findings for their cardiovascular health and with recommendation to seek specific consultation with their general practitioner or specialist. In this group a report is sent to the participants' GP.
- The LDCT image data, the coronary calcium score and % emphysema of the non-reporting group will remain confidential and will be stored for further assessment at year 1 (follow-up CT screen) and for evaluation of endpoints at year 5 and 10 (not part of this funding period).
- Apart from the randomized reporting of coronary artery calcium score and % emphysema **clinically relevant incidental findings** will be categorized in emergent (within 1-30 days), timely (within 1-6 months) or regular (>6 months) follow up. They will always be included in the CT report for the study participants.

- For emergent findings the study participant will be contacted directly by the local study team.
- Clinically non-relevant CT findings (i.e. liver or kidney cysts) not requiring physician consultation will not be included in the report.

Smoking cessation program:

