- Prior to obtaining the chest CT, all participants are counselled for smoking cessation and referred to a smoking cessation program, according to the requirements defined by the Joint Statement of the German Radiological Society. Specifically, participation in local certified smoking cessation programs such as “Das Rauchfrei Programm” (<https://www.mhh.de/pneumologie/rauchfrei>) is encouraged. In addition, an information brochure about smoking cessation and available local certified smoking cessation programs and further online information material will be given to each participant.

Biomarker program:

- All patients undergoing tissue sampling according to the LungRADS 1.1. criteria will be invited to participate in the translational biomarker program using a separate informed consent form. For the program, a blood sample for epigenetic profiling will be required, together with an exhalation sample for assessment of specific exhalatory transition markers. The findings of the Biomarker analysis will be correlated to the pathological results of the radiological finding. The exact biomarkers will be determined before the study start and included in the appendix of the protocol.
- Optionally, blood samples will be collected from the high-risk group at the 1st and 2nd screening round visit and stored in the DZL biobank for future research.

Long-term performance and cost-effectiveness:

- The Center for Health Economics Research Hannover (CHERH) develops a comprehensive microsimulation platform for the assessment of long-term performance and cost-effectiveness of nationwide lung cancer screening with LDCT based on the HANSE study data. Main objectives of the modelling study are to investigate the impact of different components of LDCT lung cancer screening on the long-term all-cause mortality and cost-effectiveness. Key components include risk score-based selection criteria, nodule management protocols, threshold values of imaging biomarkers for cardio-vascular diseases and COPD, and inclusion of smoking cessation programs.
- **Model concept:** The stochastic microsimulation model simulates virtual life histories of the HANSE study, which represents a representative sample of the German population in northern Germany. For each individual, it creates different life histories: no LC-screening, LC-screening focussing on lung cancer only, LC-screening including cardiovascular and lung comorbidity assessment, comprehensive LC-screening plus

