- **Assessment of smoking status:** Success of the smoking cessation program will be evaluated using a questionnaire, combined with a urine cotinine check (in quitters).
- **Initiation of COPD treatment:** Assessment of COPD treatment initiation during the study.
- **Consequences of screening:** Questionnaire 'Consequences of Screening' as above.

2. Evaluation

Lung cancer screening:

- The percentage of subjects receiving an adequate low-dose CT scan according to DRG guidelines will be assessed.
- For all included participants, detection rate of lung cancers will be evaluated and categorized according to LungRADS 1.1 categories.
- Detected (proven by histopathology) lung cancers will be categorized whether they were predicted by PLCO or NELSON or both. Statistical analysis will reveal potential advantages of either risk scoring methodology.
- A retrospective analysis will compare this algorithm to the PanCan nodule algorithm vs. AI for management efficiency. Based on the two alternative management algorithms patients are sorted into three management groups: (a) next surveillance scan, (b) early recall scan, or (c) diagnostic evaluation recommended. For one algorithm to be more efficient, the following criteria must both be fulfilled
 - The number of patients without lung cancer sorted in the category (a) is higher AND
 - The number of patients with lung cancer sorted into category (b) or (c) is higher.

Coronary calcium score / cardio-vascular treatment initiation:

- At the 1-year follow-up visit, the rate of initiation of cardiovascular treatment (in particular lipid-lowering) will be determined, together with BMI, and blood pressure data. Data for the calcium score reporting group will be compared to those of the non-reporting group.

Smoking cessation:

- Success of smoking cessation counseling will be based on the number of participants quitting (% quitters) within study period.
- Allocation of the participants to the different experimental groups will allow determining the influence of 'reporting' of prognostic markers (percent emphysema and coronary calcium score) on smoking cessation.

All methods will be performed according to study site SOPs.

CT analysis software (Coreline) specifications:

1. Viewer function

- LCS (Lung Cancer Screening) viewer functions

- Image display with axial, sagittal and coronal images and 3D rendering.
- Virtual slice thickness control display function for MPR (Multi-Planar Reformat) images.

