- Semi-automatic nodule segmentation and measurement.
- Follow-up nodule comparison, using automatic nodule position registration.
- Quantitative feature calculation from the nodule segmentation.
- Calculation of VDT (volume doubling time) and cancer-risk probability based on PANCAN model (Brock model).
- Structured reporting UI based on Lung RADS v1.1, with incidental findings (S Modifier) (Can be modified to conform to German requirements)
- Form-based report generation

- LAA (Lower Attenuation Area) viewer functions

- Lobe-based quantitative emphysema analysis, such as LAA-950HU and Perc15.
- Image display of axial, sagittal, coronal and 3D rendering, with LAA mask overlaid.
- Bull's eye chart for displaying LAA distribution in lobes, which are automatically segmented.
- Histogram analysis of lung parenchymal densities.
- Form-based report generation

- CAC (Coronary Artery Calcification) viewer functions

- Automatic calcification labeling and manual correction.
- AGATSTON scoring and isotropic volume scoring.
- Form-based report generation

- Automatic processing server (APS) engines

- Lung nodule detection engine (CADe, for research purpose only till CE certification)
- Lung/lobe segmentation engine for automatic nodule position determination.
- LAA analysis engine
- CAC analysis engine

- Worklist functions

- Display the important results in separate columns; (Lung-RADS category, LAA-950HU, CAC, etc.)
- Workflow management to enable double-reading capability.
- Automatic notification of high-risk (critical) reading results.
- Exporting results in CSV format (MS-Excel compatible)

2. Central registry function

- Anonymization of uploaded patient data.
- Web-based questionnaire (Specific requirements must be determined.)
- Collects all the reading results in the CLOUD database.
- CT dose management, using dose report from CT devices.
- Dashboard view to display all participating hospitals' information (charts and tables).

3. Additional function support further research work

- Radiomics feature generation from the segmented nodules.
- Exporting all the collected information in CSV format (MS-Excel compatible).
- Exporting nodule segmentation masks.
- Interface with 3rd-party research modules, such as nodule malignancy estimation.

4. Function be customized in the preparation phase of the HANSE study

- German language support.
- Customization to reflect German workflow.
- Customization of structured reporting for incidental findings.

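### The nodule-management efficiency rule needs strictly more cancers in (b)/(c), so an add-on to LungRADS 1.1 that spares recalls at an unchanged cancer count cannot be called more efficient

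*Protocol*

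**What the plan says.** Protocol section 4.2, secondary endpoint 7, sorts participants under each algorithm into three groups: (a) wait for the next surveillance scan, (b) early recall, (c) diagnostic work-up. It then states: "For one algorithm to be more efficient, the following criteria must both be fulfilled". Criterion (i) is a higher number of cancer-free participants in (a). Criterion (ii) is "The number of participants with lung cancer sorted into category (b) or (c) is higher".

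Section 5.1.2, item 2, repeats the rule with "The number of patients with lung cancer sorted into category (b) or (c) is higher", and section 6.1.2 (Evaluation) has the same strict wording. None of the three gives a margin, allows equality or classifies a tie. The synopsis (Outcomes, secondary endpoint 2) lists the two counts without a direction and does not limit count (a) to participants without cancer.

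The objective, in the synopsis and in section 2.2 (additional objective 4), is that the add-on increases efficiency. Section 5.2.2 treats all secondary parameters as explorative.

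**The concern.** Fewer unnecessary recalls with no net loss of cancers is what most readers would call a gain in efficiency. The rule cannot give that answer: with equal cancer counts it labels neither algorithm more efficient, however many recalls are spared. A stated objective could then be reported as not met although recalls fell and the number of cancers sent to recall or work-up did not.

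The design also tends to limit what an add-on can gain. Participants in the lower LungRADS categories (up to 4a) "will be scheduled for follow-up scans at intervals according to LungRADS schedule", categories 4b and 4X go to the tumour board, and the biomarker section speaks of "All patients undergoing tissue sampling according to the LungRADS 1.1. criteria". Cancers count once proven by histopathology, and the comparison is made afterwards: "A retrospective analysis will compare this algorithm to the PanCan nodule algorithm vs. AI for management efficiency". Cancers are therefore found mainly where LungRADS already sent participants to (b) or (c). This is a tendency and not a certainty: AI software supports the reading, the software also calculates the PanCan risk, and the appendix replaces the LungRADS growth definition with one based on volume doubling time.

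**Working it through.** The protocol gives no power or expected result for this endpoint, so there is no figure to reproduce. The check is one of logic, with the protocol's expected number of cancers as illustration.

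**Inputs.** The rule is from sections 4.2, 5.1.2 and 6.1.2. Expected CT-detected cancers are from section 5.3: 34 × 5000/2029 × 1.72 = 144.1, which agrees with the stated 144. Cancer-free participants: 5000 − 144 = 4,856.

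**The rule in symbols.** Both algorithms sort the same participants, so only reclassifications matter. Relative to LungRADS alone, let the add-on move
- s cancer-free participants into (a) and u out of it;
- g cancers from (a) into (b)/(c) (gained) and l cancers from (b)/(c) into (a) (lost).

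Criterion (i) is s > u. Criterion (ii) is g > l.

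**Consequences as written.**
1. Unchanged count, g = l: (ii) fails for every s from 1 to 4,856.
2. Add-on that only moves participants down to (a): g = 0, so (ii) requires 0 > l, which is never true.
3. LungRADS alone already has every proven cancer in (b)/(c): g = 0 again, so no add-on can pass.
4. Net gain of one cancer with s > u: passes.

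**Illustration.** The add-on moves a net 500 cancer-free participants to (a). The starting counts of cancers in (b)/(c) are assumed.

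| Cancers in (b)/(c): LungRADS → add-on | As written | With 'not lower' in (ii) |
|---|---|---|
| 140 → 139 | not met | not met |
| 140 → 140 | not met | met |
| 140 → 141 | met | met |
| 144 → 144 (of 144) | not met | met |

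Replacing 500 by 100 changes no entry. The two wordings differ only when the cancer count is unchanged.

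**Price of the change.** Assume that m cancers are sorted differently and that gains and losses are equally likely, so that g ~ Bin(m, 0.5). The chance of meeting (ii) then goes from P(g > l) to P(g ≥ l):
- m = 2: 0.25 to 0.75
- m = 4: 0.31 to 0.69
- m = 10: 0.38 to 0.62
- m = 20: 0.41 to 0.59

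With an odd m no tie is possible and nothing changes. An add-on without a true gain in cancer sorting thus meets (ii) more often under 'not lower'.

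**The case against.** The strongest reply is that being better on both counts is a coherent, conservative definition of 'more efficient', stated alike in three places and capable of being met. On a tie no false superiority is claimed, and a report of the two counts would show what happened. Tie handling on an explorative endpoint could also be left to the statistical analysis plan.

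Part of this stands. The rule can be met, the harm is small, and 'not lower' is the more lenient test. A net tie can also hide offsetting swaps, such as five cancers lost and five gained.

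Two parts do not stand. The protocol gives no rationale for demanding a gain on both counts, and its objective speaks only of increased efficiency. Nor is the rule left open: it is fixed in three sections, so an analysis plan that accepted a tie would contradict the protocol.

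A reader might infer that ties are likely and attach a percentage to them. The documents do not support this. They give no rate at which the algorithms disagree on cancers, and the answer turns on that rate and on the balance of gains and losses. If each of 144 cancers is sorted differently with an assumed probability of 1%, the chance of an exact tie is 38% with gains and losses equally likely, and 0.99^144 = 24% if only losses occur. At 5% the figures are 15% and 0.95^144 = 0.06%. The LungRADS-directed ascertainment limits gains and leaves losses open, so equal likelihood cannot be taken for granted.

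**Conclusion.** The point holds in a limited form. As written, an add-on that spares recalls with the same number of cancers in (b)/(c) cannot be called more efficient, and one that only moves participants down to (a) can never be. This follows from the wording alone and rests on no numerical assumption.

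Its reach is narrow: it affects only an unchanged cancer count, on an endpoint that section 5.2.2 treats as explorative. A reader might infer that the objective is unattainable in general. It is not, since an add-on that moves participants in both directions, spares recalls and gains one cancer net passes. What is at stake is the label put on one stated objective, and no tie percentage should be offered as a measure of size. The change is worth making because it is cheap and because deciding how to treat a tie after seeing the data would be post hoc.

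**What to change.** - Keep criterion (i) as 'higher' among participants without cancer.
- Change criterion (ii) from 'higher' to 'not lower' in sections 4.2 (endpoint 7), 5.1.2 (item 2) and 6.1.2 (Evaluation).
- Align the synopsis: state the direction of both counts and limit count (a) to participants without cancer.
- Report the numbers of cancers gained and lost by the add-on beside the verdict, so that offsetting swaps are visible.
- Note in the interpretation that cancers are ascertained mainly under LungRADS-directed follow-up.

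The cost is one phrase in three sections, a short edit to the synopsis and one added line of reporting. No new data are needed, and nobody's management changes, because the comparison is retrospective. A single net lost cancer still fails the add-on. The downside is that an add-on with no true gain in cancer sorting will meet (ii) more often than now, which is acceptable on an explorative endpoint if the gains and losses are shown.

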6. STUDY CONDUCT AND REGULATORY DETAILS

6.1 Data Management

6.1.1 Study Flow Chart and Plan

* Follow-up schedule

LungRADS Categories:

- 1, 2: 1 year LDCT
- 3: 6 months LDCT; VDT assessment
- 4a: 3 months LDCT; VDT assessment
- 4b, X: MDT, tissue sampling depending on the probability of malignancy and comorbidities.

Figure 1: Flow diagram of the HANSE study.

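### The nodule-algorithm efficiency rule does not distinguish early recall from diagnostic evaluation, so an algorithm can be called more efficient while diagnostic evaluations in cancer-free people rise

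*Protocol*

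**What the plan says.** Protocol section 4.2, secondary endpoint 7, compares LungRADS 1.1 alone with LungRADS 1.1 plus PanCan/AI. Under each algorithm, "participants are sorted into three management groups: (a) next surveillance scan, (b) early recall scan, or (c) diagnostic evaluation recommended". The decision rule follows: "For one algorithm to be more efficient, the following criteria must both be fulfilled". The criteria are:

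- Criterion i: "The number of participants without cancer sorted in the category (a) is higher AND"
- Criterion ii: "The number of participants with lung cancer sorted into category (b) or (c) is higher"

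Section 5.1.2, item 2, repeats the three groups ("patients are sorted into three management groups: (a) next surveillance scan, (b) early recall scan, or (c) diagnostic evaluation recommended") and the same two criteria. So does the evaluation part of section 6.1.2 ("The number of patients with lung cancer sorted into category (b) or (c) is higher"), which also states the design: "A retrospective analysis will compare this algorithm to the PanCan nodule algorithm vs. AI for management efficiency". The synopsis pools (b) and (c) in the same way, although its first count is not restricted to people without cancer.

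No section counts cancer-free participants in (c), and none separates (b) from (c) among participants with cancer. Sections 4.2 and 5.1.2 describe no other measure that would. The quality of lung nodule management is listed as an endpoint in section 4.2 without a stated measure. The cost-effectiveness model includes nodule protocols as a component but does not feed into this rule.

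**The concern.** The objective in section 2.2 is to show that adding PanCan/AI makes nodule management more efficient. Much of the burden of nodule management lies at the step from a further scan to diagnostic work-up. The protocol treats the two sides of that step differently. In section 6.1.1, LungRADS categories 3 and 4a lead to a repeat low-dose CT. The highest categories go to the tumour board: "4b, X: MDT, tissue sampling depending on the probability of malignancy and comorbidities".

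The rule defines three ordered groups and then ignores the boundary between the upper two. Two kinds of misleading verdict become possible:

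- An algorithm that sends more cancer-free people to diagnostic evaluation can be declared more efficient.
- An algorithm whose benefit is fewer such evaluations, or direct work-up of more cancers, can be declared no better.

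Section 6.4 says the study results will be taken to the national decision body for a screening programme. An efficiency claim made there should account for diagnostic evaluations.

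**Working it through.** **Inputs.** From section 5.3: 5,000 screened participants and 144 expected CT-detected cancers. The 144 reproduces: 34 × 5,000/2,029 × 1.72 = 144.1. Cancer-free: 5,000 − 144 = 4,856. The protocol gives no expected distribution over (a), (b) and (c) and no power or sample size for this endpoint, so there is no stated figure to reproduce. All category shares below are assumptions.

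**Step 1: what the rule depends on.** Within the cancer-free stratum (a) + (b) + (c) = 4,856, and within the cancer stratum the sum is 144. Both sums are the same under each algorithm because the same people are re-sorted. Hence:

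- criterion i: more cancer-free in (a) is the same as fewer cancer-free in (b) + (c);
- criterion ii: more cancers in (b) + (c) is the same as fewer cancers in (a).

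Neither expression changes when a person moves between (b) and (c). This follows from the wording alone.

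**Step 2: a modest example.** Assume 90% of cancer-free participants in (a) and 2% in (c) under the reference algorithm, and cancers split 14/40/90. The comparator moves 20 cancer-free people from (b) to (a), 50 from (b) to (c), and one cancer from (a) to (b).

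| | Cancer-free (a) | (b) | (c) | Cancers (a) | (b) | (c) |
|---|---|---|---|---|---|---|
| Reference | 4,370 | 389 | 97 | 14 | 40 | 90 |
| Comparator | 4,390 | 319 | 147 | 13 | 41 | 90 |

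Criterion i: 4,390 > 4,370, met. Criterion ii: 41 + 90 = 131 > 40 + 90 = 130, met. The comparator is more efficient under the rule, while cancer-free (c) rises by 50. The relative rise depends on the assumed share in (c):

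- 1%: 50/48.6 = 103%
- 2%: 50/97.1 = 51%
- 4%: 50/194.2 = 26%

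**Step 3: larger shifts.** Move 10 cancer-free people from (b) to (a) and half of (b) to (c), and let cancers become 12/62/70. Both criteria are met in every case (cancers in (b) + (c): 132 > 130), although fewer cancers are in (c) (70 instead of 90). Cancer-free (c) changes as follows:

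| Assumed cancer-free share in (a) | Assumed share in (c) | Cancer-free (c), reference | Cancer-free (c), comparator |
|---|---|---|---|
| 80% | 2% | 97 | 534 |
| 85% | 3% | 146 | 437 |
| 90% | 2% | 97 | 291 |
| 95% | 1% | 49 | 146 |

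**Step 4: the bound.** Criterion i makes cancer-free (b) + (c) fall by at least 1, so cancer-free (c) cannot exceed the former (b) + (c) minus 1. At 90% in (a) this is 389 + 97 − 1 = 485.

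**Step 5: the opposite case.** Keep (a) unchanged, halve cancer-free (c) from 97 to 48, so that (b) becomes 389 + 49 = 438, and let cancers become 14/10/120. Criterion i: 4,370 against 4,370, not met. Criterion ii: 130 against 130, not met. Neither algorithm is more efficient, although cancer-free (c) has halved and 30 more cancers go directly to evaluation.

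**The case against.** The pooling can be defended as a deliberate choice. It appears in the same form in three sections and the synopsis. The two criteria together act as a specificity and sensitivity requirement: more cancer-free people left until the next scheduled scan, and more cancers acted on before it. A cancer in (b) is re-scanned within months with a volume-doubling-time assessment, and the appendix sends fast-growing nodules to further work-up. Both (b) and (c) therefore act before the annual scan. This explains why (b) and (c) are pooled for cancers. It does not explain why a cancer-free person's move from a repeat scan to diagnostic evaluation should be free of cost.

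Three stronger readings are tempting, and the protocol does not support them.

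- *That the rule rewards more false positives overall.* It does not. Criterion i forces the cancer-free total in (b) plus (c) to fall. The problem is confined to shifts from (b) to (c) within a shrinking group.
- *That more cancer-free people would undergo invasive procedures.* Category (c) is a recommendation for diagnostic evaluation. Section 6.1.1 makes tissue sampling depend on the probability of malignancy and on comorbidities.
- *That collapsing three levels to two costs statistical power.* The protocol specifies no test for this endpoint; the rule compares counts. Whether a three-level test would gain or lose power depends on whether (b)/(c) moves run in the same direction as (a)/(b) moves, and the protocol says nothing about that.

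The low stakes also stand. Section 5.2.2 makes all secondary parameters exploratory, and the comparison re-sorts participants retrospectively. Nothing in the protocol suggests that PanCan or AI would in fact shift people from (b) to (c); the examples show only what the rule permits. Detailed tabulation can normally wait for a statistical analysis plan. The decision rule itself, however, is already fixed in the protocol.

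**Conclusion.** The point holds as a cheap improvement. As written, the rule cannot register any move between early recall and diagnostic evaluation. It can therefore declare an algorithm more efficient while cancer-free diagnostic evaluations rise, and it gives no credit for reducing them alone.

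The logical result needs no assumption beyond some cancer-free participants being in (b). The size does need assumptions: 97 to 147 of 4,856 rests on a 2% share in (c) and on chosen moves, and the relative rise runs from 26% to 103% for shares of 4% to 1%. None of these figures predicts what the algorithms will do.

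The consequence is limited to the wording of one exploratory, retrospective conclusion. A reader should not infer any effect on participants' care, on the primary comparison of positive predictive values, or on the key-secondary hierarchy.

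**What to change.** In section 4.2 item 7, section 5.1.2 item 2, the evaluation part of section 6.1.2 and the synopsis:

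1. Add a third condition to the efficiency definition: the number of participants without cancer in category (c) must not be higher. Both comparators in steps 2 and 3 of the working would then fail.
2. Report the paired 3x3 cross-tabulation of the algorithms compared, separately for participants with and without cancer. Show the moves between (b) and (c), and the difference in cancer-free (c) with a 95% confidence interval that respects the pairing.

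The third condition blocks the misleading positive verdict. It does not by itself credit an algorithm whose only benefit is fewer cancer-free evaluations; the tables make that benefit visible. An ordinal test that weights (a)/(b) and (b)/(c) moves equally is not needed, since equal weighting is itself a debatable choice.

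The cost is a wording change and a longer table. The three categories are already assigned under each algorithm, so no new data, readings or procedures are required. The one downside is that the claim of greater efficiency becomes slightly harder to reach.
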